**Visit 1: Screening**

- Attend the clinical research unit
- Routine clinical examination
- ECG
- Non-fasting venous blood taken for HbA1c, creatinine, lipids.
- Urine for albumin/creatinine ratio
- Urine pregnancy test in female subjects of childbearing age
- CHO counting and hypoglycaemia education revision by a qualified health care professional.
- The basal insulin dose will be reviewed and adjusted if needed.
- Questionnaires to be completed
- Continuous glucose monitor (CGM retrospective/blinded iPro2, Medtronic or Dexcom) placed in the anterior abdominal wall according to manufacturer's instructions. CGM sensor to be worn for 6-7 continuous days.
- Instructions to subjects to ensure:
  - Capillary blood glucose measurements fasting, pre-meals, post-meals and pre-bed.
  - Food diaries and physical activity record to be kept for 6 days

**Randomisation**

Subjects who fit the inclusion criteria will be randomized to either ABC4D (intervention group) or standard care (control group) in a 1:1 ratio

Standard care is defined as the bolus wizard within insulin pumps, bolus calculator in glucose meter or the ABC4D app as a standard bolus calculator (without CBR adaptation)

### **Intervention group:**

Intervention: ABC4D for 6 months

#### **Visit 2: CGM review and ABC4D start**

- Attend 7 days following visit 1
- Remove CGM, upload data to Medtronic Carelink Pro software or DiaSend/Dexcom Studio, enter and review data with subject.
- Recalculate ISF and ICR after CGM and review of different types of carbohydrates.
- Initialize CBR algorithm case base with cases derived from the CGM data and diary.
- Switch on the ABC4D device
- Instructions to subjects to ensure:
  - Capillary blood glucose measurements fasting, pre-meals, post-meals and pre-bed.
  - Accurate subject input of pre-meal capillary blood glucose, pre- or post-meal exercise (moderate or intense), type of meal absorption (fast, medium, slow), carbohydrate (CHO) amount (g) and insulin given if CBR algorithm advice not taken
  - No correction boluses for 2 hours post-meal unless clinically indicated (CBG  $>15\text{mM}$  or ketosis)
- A detailed ABC4D user guide will be given to the subject
- CGM (blinded iPro2, Medtronic or Dexcom) placed in the anterior abdominal wall according to manufacturer's instructions.

#### **Visits 3-6: Weekly CGM and update of CBR algorithm**

- Attend clinical research unit on day 7 following visit 2 and then day 14, 21 and 28.
- Upload data from the smartphone ABC4D application to the desktop PC and store it in the corresponding folder.
- Remove CGM, upload data to Medtronic Carelink Pro software or DiaSend/Dexcom Studio. The CGM data will not be disclosed to the subject.
- Export uploaded CGM data to a text file (i.e. csv) and store it in the corresponding folder.
- Using the ABC4D PC application, update the CBR algorithm case base with the uploaded data from the CGM and the data from ABC4D smartphone application. The algorithm update with new cases will be an automatic process without the research team approving each case.
- New CGM (blinded iPro2, Medtronic or Dexcom) placed in the anterior abdominal wall according to manufacturer's instructions.

#### **Visits 7-16: Monthly CGM and update of CBR algorithm**

- Blinded CGM for the last 6 days of every month for the remaining 5 months of the study

- Subject to attend the clinical research unit for insertion of the sensor at the start of blinded CGM and for upload of CGM data and update of CBR algorithm with new cases 7 days later:

*Visits 7, 9, 11, 13, 15:*

- Attend clinical research unit at start of week 8, 12, 16, 20 and 24 of the study
- New CGM (blinded iPro2, Medtronic or Dexcom) placed in the anterior abdominal wall according to manufacturer's instructions.
- All subjects will be offered the opportunity to insert the CGM themselves at home, with appropriate training, rather than attending the clinical research unit for these visits (visits 7, 9, 11, 13, 15)

*Visit 8, 10, 12, 14, 16:*

- Attend clinical research unit at end of week 8 (7 days after insertion of CGM), 12, 16, 20 and 24 of the study
- Upload data from the smartphone ABC4D application to the desktop PC and store it in the corresponding folder.
- Remove CGM, upload data to Medtronic Carelink Pro software or DiaSend/Dexcom Studio. The CGM data will not be disclosed to the subject.
- Export uploaded CGM data to a text file (i.e. csv) and store it in the corresponding folder.
- Using the ABC4D PC application, update the CBR algorithm case base with the uploaded data from the CGM and the data from ABC4D smartphone application. The algorithm update with new cases will be an automatic process without the research team approving each case.

### **Clinical review at 1 month, 3 months and 6 months:**

Review at 1 month (coincides with visit 6):

- Review of subject's diabetes control including insulin requirements, incidence of hypoglycaemia, exercise, driving etc.

Review at 3 months (coincides with visit 10):

- Review of subject's diabetes control including insulin requirements, incidence of hypoglycaemia, exercise, driving etc.
- Random venous blood taken for HbA1c
- Weight (kg)

Review at 6 months (coincides with visit 16):

- Review of subject's diabetes control including insulin requirements, incidence of hypoglycaemia, exercise, driving etc.
- Random venous blood taken for HbA1c
- Weight (kg)
- PAID score, DQOL, DTSQ and acceptability questionnaires to be completed

### **Control group:**

Intervention: Standard care for 6 months

### **Visit 2: CGM review and ABC4D start**

- Attend 7 days following visit 1
- Remove CGM, upload data to Medtronic Carelink Pro software or DiaSend/Dexcom Studio and review data with subject.
- Recalculate ISF and ICR after CGM and review of different types of carbohydrates.

### **Visits 3-8: CGM at 1, 3 and 6 months**

*Visits 3, 5, and 7:*

- Attend clinical research unit at start of week 4, 12 and 24 of the study
- New CGM (retrospective/blinded iPro2, Medtronic or Dexcom) placed in the anterior abdominal wall according to manufacturer's instructions.

*Visits 4, 6 and 8:*

- Attend clinical research unit at end of week 4 (7 days after insertion of CGM), 12 and 24 of the study.
- Remove CGM, upload data to Medtronic Carelink Pro software or DiaSend/Dexcom Studio. The CGM data will not be disclosed to the subject.

### **Clinical review at 1 month, 3 months and 6 months:**

*Review at 1 month (coincides with visit 4):*

- Review of subject's diabetes control including insulin requirements, incidence of hypoglycaemia, exercise, driving etc.

*Review at 3 months (coincides with visit 6):*

- Review of subject's diabetes control including insulin requirements, incidence of hypoglycaemia, exercise, driving etc.
- Random venous blood taken for HbA1c
- Weight (kg)

*Review at 6 months (coincides with visit 8):*

- Review of subject's diabetes control including insulin requirements, incidence of hypoglycaemia, exercise, driving etc.
- Random venous blood taken for HbA1c
- Weight (kg)
- PAID score, DQOL and DTSQ questionnaires to be completed

Usual care will be maintained for diabetes throughout the study. No concomitant medical therapies are contra-indicated, except GLP-1 analogues, SGLT2 inhibitors and gliptins. Support will be offered to any participants who have concerns about their diabetes management.

Subjects in the intervention group using the ABC4D will have the opportunity to call a physician for medical support and an engineer for technical support 24 hours a day throughout the study.

**Statistics** This is a randomised study with an intervention group and a control group. Outcomes from the study are absolutes as described above. 142 subjects with T1DM, are required to demonstrate an HbA1c difference of 0.6% with  $\alpha$  of 0.05 and 90% power (two-tailed). We aim to screen n=160 and randomise n=80 in each group. This power calculation is based on using a population mean HbA1c of 7.9% with a standard deviation of 1.1.

The sample size is comparable to other technology transfer studies, is a realistic number for recruitment and provides robust clinical validation and safety date of a new technology.

[figure not shown]
Missing, unused, and spurious data will be assessed on an individual basis and may be ignored, withdrawn or the visit may be removed from the analysis with appropriate justification adjudicated by the Principal Investigator.

**Table: Overview of activities at each visit for subjects in the intervention group**

Activity / Visit no	1	2	3	4	5	6	7	8	9	10	11	12	13	14	15	16
Insertion of CGM sensor	x	x	x	x	x		x		x		x		x		x	
Removal of CGM sensor		x	x	x	x	x		x		x		x		x		x
Food diary	x															
CGM review with subject		x														
Initialise CBR algorithm and ABC4D start		x														
Upload and synchronise CGM data and data from ABC4D application			x	x	x	x	x	x		x		x		x		x
Update CBR algorithm with new cases			x	x	x	x		x		x		x		x		
Clinical examination	x															
Weight measurement	x								x							x
Venous blood test	x								x							x
Urine test	x															
Pregnancy test	x															
ECG	x															

Questionnaire/s	X															X
Follow-up clinical review					X				X							X

### Phase 3 of ABC4D study: Overview of study

### Phase 4

**Objective:** To demonstrate efficacy of the ABC4D with real-time CGM (RT-CGM) compared to standard care with RT-CGM

Standard care is defined as the bolus wizard within insulin pumps, bolus calculator in glucose meter or the ABC4D app as a standard bolus calculator (i.e no CBR adaptation).

**Methodology** Randomised open-label study

**Primary outcome:**

HbA1c at 6 months

**Secondary outcomes:**

HbA1c at 3 months  
Post-prandial AUC at 4 hours and 6 hours  
Post-prandial AUC (<3.9) at 4 hours and 6 hours  
Episodes of hypoglycaemia within 4- and 6-hours post-prandially  
% time in target glucose (3.9-10mmol/l)  
% time in hypo- (<3.9mmol/l) and hyperglycaemia (>10mmol/l)  
Glycaemic risk: LBGI and HBGI  
Glycaemic variability: MAGE and CONGA-2  
Change in weight (kg)  
Number achieving target HbA1c (≤ 53 mmol/mol)  
24-hours insulin dose requirements  
PAID score questionnaire  
DQOL questionnaire  
DTSQ Questionnaire  
Acceptability questionnaire (non-validated)

These are validated, published metrics.

**Timescale:** Each subject will be in the study for 6 months. It is anticipated that it will take 15 months to complete the 4th phase.

**Population:** 142 subjects with T1DM, are required to demonstrate an HbA1c difference of 0.6% with  $\alpha$  of 0.05 and 90% power (two-tailed). We aim to screen n=180 and randomise n=90 in each group. This power calculation is based on using a population mean HbA1c of 7.9% with a standard deviation of 1.1.

The first 25 participants will be randomised to either the ABC4D running in semi-automatic mode (where the revisions are done using a semi-automatic process-see page 23) or a standard bolus calculator. The remaining participants will be randomised to either the fully automated ABC4D (where revisions are fully automated) or a standard bolus calculator. Screening 180 participants will ensure that at least 142 participants are included to enable demonstration of a significant difference between the fully automated ABC4D system and a standard bolus calculator.

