### ***Randomisation***

Subjects who fit the inclusion criteria will be randomized to either ABC4D (intervention group) or standard care (control group) in a 1:1 ratio. Both groups will be using RT-CGM.

Standard care is defined as the bolus wizard within insulin pumps, bolus calculator in glucose meter or the ABC4D app as a standard bolus calculator (without CBR adaptation).

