### Visit 2: CGM review and control study start

- Attend 4 weeks after visit 1
- Remove CGM, upload data to DiaSend/Dexcom Studio software (subject can do upload the data at home prior to attending the visit) and review data with subject.
- Adjust ICR, ISF and basal rates if deemed necessary based on CGM data.

Follow-up clinic visits at 1 month, 3 months and 6 months:

### Visit 3

Review at 1 month:

- Review of subject's diabetes control including insulin requirements, incidence of hypoglycaemia, exercise, driving etc.

### Visit 4

Review at 3 months:

- Review of subject's diabetes control including insulin requirements, incidence of hypoglycaemia, exercise, driving etc.
- Random venous blood taken for HbA1c
- Weight (kg)

### Visit 5

Review at 6 months:

- Review of subject's diabetes control including insulin requirements, incidence of hypoglycaemia, exercise, driving etc.
- Random venous blood taken for HbA1c
- Weight (kg)
- PAID score questionnaire and acceptability questionnaire to be completed

Usual care will be maintained for diabetes throughout the study. No concomitant medical therapies are contra-indicated, except GLP-1 analogues, SLGT2 inhibitors and gliptins. Support will be offered to any participants who have concerns about their diabetes management.

Subjects in the intervention group using the ABC4D will have the opportunity to call a physician for medical support and an engineer for technical support 24 hours a day throughout the study.

*Statistics* This is a randomised study with an intervention group and a control group. Outcomes from the study are absolutes as described above. 142 subjects with T1DM, are required to demonstrate an HbA1c difference of 0.6% with  $\alpha$  of 0.05 and 90% power (two-tailed). We aim to screen n=160 and randomise n=80 in each group. This power calculation is based on using a population mean HbA1c of 7.9% with a standard deviation of 1.1.

The sample size is comparable to other technology transfer studies, is a realistic number for recruitment and provides robust clinical validation and safety date of a new technology.

[figure not shown]
Missing, unused, and spurious data will be assessed on an individual basis and may be ignored, withdrawn or the visit may be removed from the analysis with appropriate justification adjudicated by the Principal Investigator.

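### Phase 4 states and sizes its claim for fully automated ABC4D, but its defined groups pool two modes and the Statistics paragraph does not say how the first 25 participants are used

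*Combined protocol and SAP*

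**What the plan says.** The Phase 4 Population paragraph describes two randomised cohorts in sequence. "The first 25 participants will be randomised to either the ABC4D running in semi-automatic mode" or a standard bolus calculator; the remaining participants go to fully automated ABC4D or a standard calculator. The section on case base revision and adaptation repeats the split as 25 and then 155.

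The Population paragraph says "142 subjects with T1DM, are required to demonstrate an HbA1c difference of 0.6" percentage points, at two-sided alpha 0.05 and 90% power, from a "population mean HbA1c of 7.9% with a standard deviation of 1.1". It then says what recruiting 180 is for: at least 142 participants, enough to show "a significant difference between the fully automated ABC4D system and a standard bolus calculator".

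The groups are defined without reference to mode:
- Population: "We aim to screen n=180 and randomise n=90 in each group".
- Phase 4 Randomisation: ABC4D or "standard care (control group) in a 1:1 ratio".
- Phase 4 Statistics: "This is a randomised study with an intervention group and a control group". This paragraph gives a target of 160, or 80 per group, and names no test, model or analysis set.

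The Phase 4 Objective also refers to ABC4D without a mode.

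**The concern.** The claim and the sample size belong to one mode, while the groups contain two. An analyst working from the Statistics paragraph has only a two-group structure to follow, and using it would estimate a mixture of the two modes. An analyst working from the Population paragraph would set the first 25 aside. A third might drop only the semi-automatic users and keep their 12 to 13 controls, who were not randomised alongside the fully automated arm. The plan does not choose among these.

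The choice matters more because Phase 4 is open-label and missing or spurious data are to be handled case by case by the Principal Investigator. With the primary set undefined, it could be settled after results are known. The lower total in the Statistics paragraph adds a second problem: on that figure, the fully automated cohort is smaller than the plan's own requirement.

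**Working it through.** **Inputs.** Difference 0.6, SD 1.1, two-sided alpha 0.05, power 90%, and required total 142 (Population and Statistics paragraphs); 1:1 allocation (Randomisation); first cohort 25 (Population, case base revision); planned total 180 (Population) or 160 (Statistics). The documents give no dropout rate and no effect by mode.

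**1. The plan's own figure.** n per arm = 2 × (1.960 + 1.282)² × 1.1² / 0.6² = 70.6, rounded up to 71, so 142 in total. The stated figure is reproduced. (A t-based calculation gives 72 per arm, 144 in total.)

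**2. Which contrast the 142 fits.** 180 − 25 = 155, which exceeds 142 and matches the 155 in the case base revision section. The Population arithmetic is therefore consistent with analysing the fully automated cohort alone. With the Statistics paragraph's total, 160 − 25 = 135, which is 7 short of 142 before any loss.

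**3. Power for a difference of 0.6.** Power = Φ(0.6 / [1.1 × √(2/n)] − 1.96), with n per arm.

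| Total analysed | Meaning | Normal approximation | t-test |
|---|---|---|---|
| 180 | both modes pooled, each with effect 0.6 | 95.5% | 95.3% |
| 155 | fully automated cohort, from 180 | 92.4% | 92.1% |
| 142 | stated requirement | 90.1% | 89.8% |
| 135 | fully automated cohort, from 160 | 88.7% | 88.2% |
| 117 | fully automated cohort if the 142 include the first 25 | 83.9% | not run |

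The margin in the 155 is 155 − 142 = 13 participants, or 13/155 = 8.4%.

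**4. Share of the ABC4D arm in the other mode.** Under 1:1 allocation about 25/2 = 12.5 of the first cohort receive semi-automatic ABC4D: 12.5/90 = 13.9%, or 12.5/80 = 15.6%.

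**5. What pooling would estimate.** Pooled effect = 0.139 × semi-automatic effect + 0.861 × fully automated effect, at 180. Both effects below are assumptions, with the fully automated effect set at 0.6.

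| Assumed semi-automatic effect | Pooled effect | Power at 180 (normal) |
|---|---|---|
| 0 | 0.517 | 88.3% |
| 0.3 | 0.558 | 92.6% |
| 0.6 | 0.600 | 95.5% |
| 0.9 | 0.642 | 97.5% |

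The pooled value can lie on either side of the fully automated effect, and equals it if the modes perform alike.

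**The case against.** A reader might infer that the Statistics section commits the trial to analysing the wrong contrast. The documents do not support that. The paragraph describes the groups but specifies no analysis, and its sentence about an intervention and a control group also appears in the Phase 3 Statistics text. Its 160 and 80 per group match Phase 3 too, which is consistent with text carried over without updating. The Population arithmetic itself points to a fully automated analysis.

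Nor does pooling break the randomisation. Both cohorts are allocated 1:1 against a standard calculator, so ABC4D v standard across all participants is a valid randomised comparison, and it answers the mode-free Objective. Non-concurrent controls arise only if semi-automatic users are dropped and their controls kept, which the plan nowhere proposes.

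The modes may also differ little. The case base revision section has the study team approve the adaptation summary without limiting this to one mode, and the Trial Objectives section describes Phase 4 case retrieval as semi-automatic throughout. The size of any distortion is therefore unknown.

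All of this stands, and it limits the point to a mismatch between the claim and the defined groups. It does not remove that mismatch: the Population paragraph names the fully automated mode as the thing to be demonstrated, and no defined group or analysis set isolates it.

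**Conclusion.** The concern holds in this form: the Phase 4 claim and its 142 participants are stated for fully automated ABC4D v a standard calculator, the defined groups pool both modes, and the use of the first 25 and their controls is unspecified. Analysis by the stated groups would place about 14% semi-automatic users in an ABC4D arm of 90 (16% of 80). If the fully automated effect is 0.6 and the semi-automatic effect lies between 0 and 0.6, the pooled effect is 0.52 to 0.60. Those effects are assumed, and the direction would reverse if the semi-automatic mode did better. Apart from any mode effect, the 160 in the Statistics paragraph leaves 135 for the claimed contrast, with about 88% power at no loss, against a target of 90%. This should be settled before analysis; the design can stay as it is.

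**What to change.** In the Phase 4 Statistics section:
- Make the primary comparison fully automated ABC4D v standard calculator among participants randomised from number 26 onward, using only the controls randomised in that same cohort.
- Report the first 25, both arms, separately.
- Combine the cohorts only in a supportive analysis stratified by cohort, so that each mode is compared with its own controls.
- Change 160 and 80 per group to 180 and 90 per group, to agree with the Population paragraph and the 155 in the case base revision section.

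The cost is some wording, one model term and a little power: about 92% at 155 instead of about 95% at 180 pooled. At most 13 participants (8.4%) can be lost before the primary cohort falls below 142. Since the plan gives no dropout rate, the sponsor should state one and check it against that margin.

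If the sponsor prefers the pooled comparison as primary, it should instead restate the Population claim as ABC4D in either mode and stratify the analysis by cohort. The total still has to be reconciled.

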**Subject inclusion criteria:**

- Adults ≥18 years of age
- Diagnosis of T1DM for > 1 year
- On MDI using a basal-bolus insulin regime or continuous subcutaneous insulin infusion (insulin pump)
- Structured education done
- HbA1c ≥ 48mmol/mol and ≤ 86mmol/mol
- No severe hypoglycaemia (defined as needing 3rd party assistance) in previous year

**Subject exclusion criteria:**

- Recurrent severe hypoglycaemia
- Pregnant or planning pregnancy

- Breastfeeding
- Enrolled in other clinical trials
- Have active malignancy or under investigation for malignancy
- Addison's Disease
- Gastroparesis
- Autonomic neuropathy
- Concomitant use of GLP-1 analogues, SGLT2 inhibitors and gliptins
- Visual impairment
- Reduced manual dexterity

***Subject withdrawal criteria:***

- Loss of capacity to give informed consent
- Cessation of MDI of insulin as usual care for T1DM
- Recurrent severe hypoglycaemia
- Terminal illness

Withdrawal will be immediate and subjects will be followed up in the appropriate out-patient diabetes clinic within 4 weeks of withdrawal

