## Phase 4 of ABC4D study: Overview of study

**The following information applies to all four phases of the study:**

***Potential risks and benefits***

The potential risks and burdens for research participants are as follows:

At the beginning of each phase of the study there is a venous blood test and in addition the 1st phase includes insertion of an intravenous cannula. These have the potential to cause discomfort. This will be minimised by experienced research personnel and appropriate use of equipment.

During the studies, subjects will have a subcutaneous CGM sensor inserted. Sensor insertion can be associated with some discomfort but the insertion devices are spring-loaded with introducers, making the process rapid and often painless. Any discomfort will be minimised by adhering to manufacturer's instructions.

During the time subjects are using the ABC4D there is a risk from the new technology. The ABC4D may suggest an insulin dose too high or too low potentially resulting in hypo- or hyperglycaemia. In the Phase 1 study subjects are closely monitored in a controlled supervised environment to ensure safety of the ABC4D. In addition, subjects will be given contact phone numbers to call a physician for medical support and an engineer for technical support 24 hours a day throughout phase 2 and 3 of the study.

Insulin will be administered subcutaneously by the subject as per their usual basal-bolus insulin regime. The subcutaneous route is the standard route of insulin administration in T1DM irrespective of whether they are on MDI or pump therapy.

It is acknowledged that the clinical schedule is demanding of subject's time and includes frequent visits to the clinical research unit. This inconvenience is necessary to adequately and safely validate the device. We will minimise the burden as much as possible by making every effort to schedule visits around subject's lifestyles, and by being flexible with attendances at the St Mary's, Charing Cross or Hammersmith campuses of Imperial College Healthcare NHS Trust.

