For phase 3 and 4 of the study a data monitoring committee will be convened to assess the data collected throughout the study. This committee will comprise of the PI ([name]), [name], [name], a lay member, an independent diabetologist and an independent scientist and will meet twice a month.

**Safety** During intercurrent illness, subject visits will be postponed as insulin requirements will be altered. Adverse events will be reported to the REC, the sponsor and the Principal Investigator immediately. Full reports will be submitted through the Imperial College Healthcare Datix system. Subjects will be followed-up after one week following an adverse event and thereafter in the diabetes clinic or any other clinically indicated follow up.

**Direct Access to Source Data/Documents** The investigator(s)/institution(s) will permit trial-related monitoring, audits, IRB/IEC review, and regulatory inspection(s), providing direct access to source data/documents.

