## Regulatory Issues

**Ethics Approval** The Chief Investigator has obtained approval from the London-Chelsea Research Ethics Committee. The study must be submitted for Site Specific Assessment (SSA) at each participating NHS Trust. The Chief Investigator will require a copy of the Trust R&D approval letter before accepting participants into the study. The study will be conducted in accordance with the recommendations for physicians involved in research on human subjects adopted by the 18th World Medical Assembly, Helsinki 1964 and later revisions.

**Consent** Consent to enter the study must be sought from each participant only after a full explanation has been given, an information leaflet offered and time allowed for consideration. Signed participant consent should be obtained. The right of the participant to refuse to participate without giving reasons must be respected. After the participant has entered the study the clinician remains free to give alternative treatment to that specified in

the protocol at any stage if he/she feels it is in the participant's best interest, but the reasons for doing so should be recorded. In these cases the participants remain within the study for the purposes of follow-up and data analysis. All participants are free to withdraw at any time from the protocol treatment without giving reasons and without prejudicing further treatment.

**Confidentiality** The Chief Investigator will preserve the confidentiality of participants taking part in the study and is registered under the Data Protection Act.

**Indemnity** Imperial College London holds negligent harm and non-negligent harm insurance policies which apply to this study.

**Sponsor** Imperial College London will act as the main Sponsor for this study. Delegated responsibilities will be assigned to the NHS trusts taking part in this study.

**Funding** This study is being funded by the Biomedical Research Council.

**Audits** The study may be subject to inspection and audit by Imperial College London under their remit as sponsor and other regulatory bodies to ensure adherence to GCP and the NHS Research Governance Framework for Health and Social Care (2nd edition).

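### Phases 3 and 4: immediate subject withdrawal for recurrent severe hypoglycaemia does not separate stopping the device from leaving the study, so the 6-month HbA1c may be lost for an outcome-related reason

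*Combined protocol and SAP*

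**What the plan says.** The subject withdrawal criteria for Phase 3 and Phase 4 carry the same four-item list, and recurrent severe hypoglycaemia is one of the items. The consequence is the same in both phases: "Withdrawal will be immediate and subjects will be followed up in the appropriate out-patient diabetes clinic within 4 weeks of withdrawal". Neither list says what the person is withdrawn from, and neither mentions the 3- and 6-month reviews at which HbA1c is taken.

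Three other places bear on this:

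- **Potential risks and benefits** (all phases) names the hazard: "The ABC4D may suggest an insulin dose too high or too low potentially resulting in hypo- or hyperglycaemia".
- **Safety** (all phases) sets the follow-up after an adverse event: "Subjects will be followed-up after one week following an adverse event and thereafter in the diabetes clinic or any other clinically indicated follow up". This too is clinical follow-up and names no trial assessment.
- **Regulatory Issues, Consent** (all phases) says that once a participant has entered, "the clinician remains free to give alternative treatment to that specified in" the protocol, and continues: "In these cases the participants remain within the study for the purposes of follow-up and data analysis". The next sentence describes voluntary withdrawal: "All participants are free to withdraw at any time from the protocol treatment without giving reasons and without prejudicing further treatment".

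The Statistics paragraphs of Phases 3 and 4 leave missing data to case-by-case adjudication by the Principal Investigator.

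**The concern.** Stopping the device after repeated severe hypoglycaemia is right for safety. Stopping measurement is not needed for safety, and the withdrawal text does not distinguish the two. Unlike loss of capacity or terminal illness, this criterion is tied to the outcomes: hypoglycaemia measures are secondary outcomes in both phases, the protocol names hypoglycaemia as a device risk, and the primary outcome is HbA1c at 6 months.

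If site staff treat the criterion as leaving the study, participants possibly harmed by the device drop out of the comparison that judges it. No rule then fixes how the missing 6-month value is handled, and both phases are open label. Bias follows if withdrawal rates, or the outcomes of those withdrawn, differ by arm. The documents give neither.

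**Working it through.** **1. The texts side by side**

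| Text | Trigger | What continues |
|---|---|---|
| Withdrawal criteria, Phases 3 and 4 | Recurrent severe hypoglycaemia, by name | Clinic review within 4 weeks; nothing else named |
| Safety | Any adverse event | Follow-up at one week, then clinic |
| Consent | Clinician gives alternative treatment | Follow-up and data analysis |
| Consent | Participant chooses to withdraw from protocol treatment | Not stated |

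Only the third row promises continued trial follow-up. Its trigger is a treatment change, and it refers neither to the withdrawal criteria nor to the scheduled assessments. The first row is the specific rule for this event. The two texts conflict, or are at least ambiguous.

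**2. The plan's sample size**

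Inputs from the Phase 3 and 4 Statistics paragraphs: difference 0.6, SD 1.1, two-sided alpha 0.05, power 90%.

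n per arm = 2 × (1.960 + 1.282)² × 1.1² / 0.6² = 70.6, so 71 per arm and 142 in total. The plan's figure reproduces. (The t-based answer is 71.6, so 72 per arm.)

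Planned numbers are 80 per arm in Phase 3. Phase 4 gives 90 per arm under Population and 80 under Statistics, so both are used below.

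**3. Shift in an arm mean for HbA1c**

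No event rate, arm difference or outcome gap is given. Assumptions: k = 1 to 4 people withdrawn in one arm and none in the other; their 6-month HbA1c would differ from that of retained participants by 0.5 to 1 SD (0.55 to 1.1 points), in either direction.

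Shift = (k/n) × gap

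| n per arm | k = 1 | k = 4 |
|---|---|---|
| 80 | 0.007 to 0.014 | 0.028 to 0.055 |
| 90 | 0.006 to 0.012 | 0.024 to 0.049 |

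Largest value against the target: 0.055 / 0.6 = 9.2%. Against the standard error of the difference at 80 per arm, 1.1 × √(2/80) = 0.174, it is 0.055 / 0.174 = 0.32 standard errors.

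**4. Power (two-sample t test, difference 0.6, SD 1.1, two-sided 0.05)**

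| Planned per arm | No loss | 1 lost in one arm | 4 lost in one arm |
|---|---|---|---|
| 80 | 92.9% | 92.8% | 92.3% |
| 90 | 95.3% | 95.2% | 94.9% |

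The largest fall is 92.9 − 92.3 = 0.6 percentage points.

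**5. Hypoglycaemia outcomes**

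The secondary outcome lists give no time window. As a limiting case, take % time below 3.9 mmol/l over a window wholly after the stop, and assume that those withdrawn would have had r = 0.5 to 2 times the retained participants' value. With f = k/n:

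observed / full − 1 = 1 / (1 + f(r − 1)) − 1

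For 4 of 80, r = 0.5 gives +2.6% and r = 2 gives −4.8% (relative). A window that includes CGM from before the stop would dilute this, and such data would normally exist. In Phase 3, sensors are worn weekly at first and then monthly in the intervention arm, and at 1, 3 and 6 months in the control arm. In Phase 4, CGM runs throughout in both arms. The clinical reviews in both arms also cover the incidence of hypoglycaemia.

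**The case against.** The strongest reply is that the Consent paragraph already settles the matter. It applies to all four phases. A clinician who stops ABC4D after repeated severe hypoglycaemia is giving alternative treatment in the participant's interest, and such participants stay in follow-up and analysis. The paragraph also describes voluntary withdrawal as being from protocol treatment. On this reading, only a cross-reference is missing.

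Much of this stands. The paragraph may well cover these people, and it shows that the protocol accepts retention after a treatment change. But it does not mention the withdrawal criteria, and a coordinator applying the more specific rule could reasonably cancel the remaining visits.

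It also stands that immediate withdrawal is a legitimate safety rule, that it applies equally to both arms, and that events should be rare. Entry requires "No severe hypoglycaemia (defined as needing 3 rd party assistance) in previous year", and Phase 4 adds a 4-week run-in and CGM alarms.

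A reader might infer that the withdrawal text itself ends the 3- and 6-month assessments. It does not say so: it sets a clinic review within 4 weeks and does not exclude later visits. A reader might also infer a known bias for or against the device. The documents give no rates by arm and no outcomes for those withdrawn, so no direction can be stated.

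**Conclusion.** The point holds as an ambiguity with a plausible harmful reading, not as a design that is shown to discard outcomes. The withdrawal rule and the Consent paragraph do not agree on what happens after recurrent severe hypoglycaemia, and the reading that loses the 6-month HbA1c does so for an outcome-related reason.

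The expected effect is small: at most 0.055 HbA1c points on an arm mean and about 0.6 percentage points of power. These figures rest wholly on the assumed 4 v 0 withdrawals and the assumed 1 SD gap. Larger biases need withdrawal rates that nothing in the documents supports for this event. Severity is low: a change that could be made and is worth making because it costs so little.

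**What to change.** In Phases 3 and 4, replace subject withdrawal for this one criterion with wording to this effect:

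- Recurrent severe hypoglycaemia stops ABC4D in the intervention arm. In the control arm, insulin dosing is changed as clinically needed. The usual bolus calculator need not be stopped, because the comparator is ordinary care: "Standard care is defined as the bolus wizard within insulin pumps, bolus calculator in glucose meter", or the app without adaptation.
- In both arms the clinic review within 4 weeks stays. With continuing consent, the participant also has the scheduled 3- and 6-month HbA1c, with weight and questionnaires where scheduled.
- CGM after the stop is optional.
- The participant is analysed in the allocated group, in line with the Consent paragraph.
- The numbers of such stops and of severe hypoglycaemia events are reported by arm.

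The other withdrawal criteria are left as they are.

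The cost is amendment wording and one or two already planned visits for a few people; no extra sensor use is required. The downside is that outcomes after the stop include time off the device, which is the ordinary consequence of analysing as allocated.
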